9.7.1.2 Primary Analysis

The primary analysis will be performed at the end of data collection including all respondents and OBI administrations fulfilling selection criteria. All statistical analyses planned in the SAP approved prior to initiation of the statistical analysis will be performed.

9.7.2 Planned Method of Analysis

9.7.2.1 General Considerations

All analyses will be descriptive. Continuous variables will be summarised by mean, median, standard deviation, Q1, Q3, minimum, maximum, 95% confidence intervals and number of valid and missing values for outcome variables. Categorical variables will be summarised by number and percentage of responses per category and 95% confidence intervals for outcome variables. The number of valid and missing values will be reported for each variable. Missing values will not be included in the denominator to calculate the percentage of responses per response category. Additional details about management of missing values per study variable will be described in the SAP.

9.7.2.2 Missing or Incomplete Data and Lost to Follow-up

Given the real-world nature of the data and the descriptive purpose of the study imputation methods for missing or incomplete data will be not used.

Date: 10 April 2019 Page 30 of 61

9.7.2.3 Descriptive Analysis

9.7.2.3.1 Description of Study Enrollment

A description of the number and percentage of respondents and OBI applications will be reported:

- Study population: All respondents invited to participate in the study.
- Eligible set: All respondents included in the study population who fulfill all selection criteria. Detailed information about eligible criteria not fulfilled will be also reported.
- Enrolled set: All respondents included in the eligible set who accept to participate in the study or who sign the informed consent.
- Full analysis set of respondents: Will include all respondents enrolled in the study
 who complete the questionnaire corresponding to at least one OBI administration
 and have valid responses to allow for the assessment of the primary objective.
- Full analysis set of OBI administrations: Will include all OBI administrations
 monitored by respondents included in the full analysis set of respondents and for
 which the corresponding questionnaire is completed and allows for the
 assessment of the primary objective.

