The source population will be the primary person responsible for monitoring the OBI after application, ie, patients or, if appropriate, their caregivers. This person will be defined as the "respondent". For every patient receiving OBI for Neulasta, the respondent will be defined at the time of study inclusion. Respondents can be included in the study multiple times at different chemotherapy cycles in which the OBI is being prescribed to the patient, if eligibility criteria including informed consent are met. In subsequent administrations of the questionnaire, data will only be collected to meet the secondary objective regarding medication errors (via a partial respondent questionnaire).

HCPs working at sites in which the OBI is being prescribed or expected to be prescribed will be approached for participation in the study.

Summary of Subject Eligibility Criteria

- Inclusion criteria
 - Respondent (ie, patients or caregivers primarily responsible for monitoring the OBI) who agrees to be contacted for the questionnaire.
 - Respondent aged 18 or more years.
 - Respondent with no cognitive impairment.
 - Respondent who can read and understand the language in which the study is being conducted and in which the PAC is provided.

Date: 10 April 2019 Page 12 of 61

Patient has been prescribed the OBI for Neulasta delivery for their current chemotherapy cycle.

Patient and respondent provide their written informed consent to participate in the study.

Exclusion criteria

Product: Pegfilgrastim

- Respondent personally works, or works on a consultancy basis, for any pharmaceutical company or advertising/research agency.
- Patient has participated or is participating in a clinical trial of Neulasta administered via OBI.

Follow-up

No follow-up is conducted after the questionnaire administration in this cross-sectional study.

Variables

- Respondent demographics and characteristics, including age, sex, educational level, self-reported language skills, self-reported confidence to monitor the OBI, health literacy - using the guestions from the Brief Health Literacy Screen (BHLS) questionnaire (Chew et al. 2004) -, respondent type (patient or caregiver)
- Respondent prior use and/or monitorisation of the Neulasta OBI
- Details of respondent receipt and use of the PAC
- Respondent reported awareness of key safety messages in the PAC
- Respondent reported behavioural intent to carry out recommended actions as described in the PAC

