8.1 Primary

The primary objective of the study is to assess respondent awareness of key safety messages and behavioural intent to carry out recommended actions as described in the PAC.

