8.2 Secondary

The secondary objectives of this study are:

- To determine if the respondent received the PAC.
- To estimate the proportion of OBI administrations associated with medication error.

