9.1 Study Design

An observational cross-sectional study based on primary data collection is planned in a number of EU countries after the introduction of the OBI for Neulasta in the EU market.

The source population will be the primary person responsible for monitoring the OBI after application by the HCP, ie, patients or, if appropriate, their caregivers. This person will be defined as the "respondent". For every patient receiving OBI for Neulasta, the respondent will be defined at the time of study inclusion. In case the caregiver is identified as the respondent, the caregiver will need to be present at the time of OBI application and study inclusion.

Participating HCPs will assess the eligibility of respondents in a consecutive manner according to the date of OBI application. This approach is designed to minimise selection bias and to allow for the study results to be generalizable to the wider population of OBI treated patients. Upon patient and respondent consent to participate in the study, the HCP will immediately record in the study electronic case report form (eCRF) the information of the time and day of OBI application. Respondents will be contacted from approximately 27 to 72 hours after the OBI application (ie, approximately 0 to 45 hours after the Neulasta dose is expected to be delivered through the OBI) and asked to respond to a questionnaire. The questionnaire will be administered either by paper or online. Additionally, HCPs will be requested to provide data on their observations (eg, time and date of OBI administration, medication errors at the time OBI application, etc.) at each application of OBI for a participating patient in the eCRF.

Respondents can be included in the study multiple times at different chemotherapy cycles in which the OBI is being prescribed to the patient, if eligibility criteria including informed consent are met (Section 9.2.3). In subsequent administrations of the questionnaire, data will only be collected to meet the primary objective regarding medication errors (via a partial respondent questionnaire).

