9.3 Variables

Variables collected in the respondent questionnaire, to be administered approximately 27 to 72 hours after OBI application, will include:

- Respondent demographics and characteristics, including age, sex, educational level, self-reported language skills, self-reported confidence to monitor the OBI, health literacy - using the questions from the Brief Health Literacy Screen (BHLS) questionnaire (Chew et al. 2004) -, respondent type (patient or caregiver)
- Respondent prior use and/or monitorisation of the Neulasta OBI
- Details of respondent receipt and use of the PAC
- Respondent reported awareness of key safety messages in the PAC (eg, OBI alerts for Neulasta dose delivery or issues, time of removal of OBI, etc.)
- Respondent reported behavioural intent to carry out recommended actions as described in the PAC (eg, symptoms related to infection, issues with Neulasta dose delivery via the OBI, etc.)
- Device issues experienced by the patient (eg, whether the device came loose, red light came on, leakage, etc.) and any resulting actions*
- Symptoms of adverse events potentially related to medication errors experienced by the patient (eg, fever, chills, sweating, etc.) and related consultations with HCPs*
- Details on dose delivery (eg, expected dose delivered on time, partial dose received, etc.)*
- Occurrence of a replacement G-CSF dose (eg, type of replacement and timing)*

In addition, the HCP will report the following variables through an eCRF, to be completed at the time of respondent identification and consent:

- HCP and site characteristics (only reported once per HCP)
- HCP awareness of methods to obtain the PAC
- Date and time of OBI application
- Device issues observed by the HCP at the time of OBI application (eg, the device coming loose, problems filling the device, leakage, etc.)

^{*} Indicates variables to be collected in the partial respondent questionnaire

Date: 10 April 2019 Page 22 of 61

9.3.1 **Exposure Assessment**

Product: Pegfilgrastim

Patients included in the study will have been administered the OBI as per routine clinical practice.

9.3.2 **Outcome Assessment**

The primary endpoint for the respondent questionnaire is:

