9.7 Data Analysis

9.7.1 Planned Analyses

The statistical analysis will be conducted with SAS® statistical software or R. A detailed statistical analysis plan (SAP) will be prepared and accepted before the data analysis initiation.

All the respondents participating in the study who meet the eligibility criteria will be included in the sample of respondents in which reception of the PAC, awareness of key safety messages and behavioural intent to carry out recommended actions as described in the PAC will be assessed. Respondents monitoring more than one OBI application in the context of the study will complete reception of PAC, awareness of key safety messages and behavioural intent sections only for the first OBI application

Date: 10 April 2019 Page 29 of 61

All OBI applications reported by participant respondents will be included in the sample of treatments to estimate the proportion of OBI applications associated with medication error. OBI applications for Neulasta doses that have not been delivered (due to medication error) will be also included in the full analysis set of OBI applications. More than one OBI application can be reported for the same respondent.

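### As written, the analysis set for medication errors excludes repeat OBI applications by the same respondent, contradicting the plan's statement that all reported applications count

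*Protocol*

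**What the plan says.** Section 9.7.2.3.1 puts two conditions on the full analysis set of OBI administrations. The respondent must belong to the full analysis set of respondents, which requires valid responses for the primary objective. The administration must also be one for "which the corresponding questionnaire is completed and allows for the" assessment of the primary objective.

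Section 8.1 states that the primary objective "is to assess respondent awareness of key safety messages and behavioural intent to carry out recommended actions as described in the PAC". Medication errors are a secondary objective in section 8.2: "To estimate the proportion of OBI administrations associated with medication error".

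For repeat applications by the same respondent, section 9.3 marks the retained items with an asterisk, explained as "Indicates variables to be collected in the partial respondent questionnaire". The marked items are device issues, symptoms, dose delivery and replacement dose. Awareness and intent are not marked. Section 9.7.1 agrees: respondents with more than one application complete the "awareness of key safety messages and behavioural intent sections only for the first OBI application".

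On which applications count, section 9.7.1 says "All OBI applications reported by participant respondents will be included in the sample of treatments to estimate the proportion of OBI applications" with medication error. The abstract says the same. Both allow more than one application per respondent.

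On the purpose of the repeat data, the abstract says "data will only be collected to meet the secondary objective regarding medication errors". Section 9.1 says "In subsequent administrations of the questionnaire, data will only be collected to meet the primary objective regarding medication errors (via a partial respondent questionnaire", and section 9.2.5 also uses the label primary.

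**The concern.** Two parts of the protocol give different denominators for the same estimate. The set definition ties each administration to a questionnaire that can assess awareness and intent, and a partial questionnaire cannot. A programmer following section 9.7.2.3.1 would keep first applications only (per respondent). One following section 9.7.1 would keep all of them.

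The respondent-level condition adds a second exclusion. A respondent who reports a leaking or failed device, but has no valid awareness and intent answers, is removed together with all applications he or she monitored. This selects the medication-error sample on completion of the knowledge items. Sections 9.7.2.2 and 9.7.2.5 plan neither imputation nor a sensitivity analysis, so nothing planned would show the effect.

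Section 7.2 says that the study was developed to measure the rate of medication errors following the regulatory review. The affected estimate is therefore one of the study's reasons for existing, although it is formally secondary.

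**Working it through.** **Does a partial questionnaire meet the condition?**

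1. Condition (9.7.2.3.1): the administration's own questionnaire must allow assessment of the primary objective.
2. Primary objective (8.1) and primary endpoint (9.3.2): awareness and behavioural intent.
3. Partial questionnaire (9.3): no awareness or intent items. Section 9.7.1 confirms that they are asked at the first application only.
4. So a partial questionnaire cannot meet the condition, and same-respondent repeats fall outside the set.
5. Exception (9.1): if a different person monitors a later application of the same patient, that person completes a full questionnaire and counts as a new respondent. That application stays in.

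Under this reading the comparison of initial with subsequent applications in section 9.7.2.4 has no partial-questionnaire data.

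**Size.** Inputs from section 9.5: 80 patients, 3.5 OBI uses on average, a maximum of 280 applications.

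- Plan's figure reproduced: 80 × 3.5 = 280.
- Kept under the literal definition, one application per respondent: about 80.
- Lost: 280 − 80 = 200, and 200/280 = 71%. This is an upper bound, because 280 is a maximum, section 9.2.3.1 lets respondents enter after earlier OBI use, and a new respondent's full questionnaire stays in.

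**Precision with independent applications** (exact Clopper–Pearson 95% limits). The protocol gives no expected medication-error proportion, so 5% is an assumption, with 10% and zero observed errors as a range.

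| Scenario | n = 280 | n = 80 |
|---|---|---|
| 5% | 14/280: 2.8–8.2% | 4/80: 1.4–12.3% |
| 10% | 28/280: 6.8–14.1% | 8/80: 4.4–18.8% |
| No errors seen, upper limit | 1.3% | 4.5% |

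The only device-failure figure in the protocol is 5 unsuccessful of 297 administrations in healthy subjects (section 7.1), or 1.68%. It is not a medication-error rate in routine care and serves only as an illustration. Expected events are 280 × 0.0168 = 4.7 against 80 × 0.0168 = 1.3. The chance of seeing none, (1 − 5/297)^n, is 0.9% against 26%.

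**Allowing for within-patient correlation.** With 3.5 applications per patient the design effect is 1 + 2.5ρ, the effective sample size is 280/(1 + 2.5ρ), and the half-width is 1.96 × √(0.05 × 0.95 / effective n). The value of ρ is assumed.

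| ρ | Effective n | Half-width at 5% (points) |
|---|---|---|
| 0 | 280 | 2.6 |
| 0.1 | 224 | 2.9 |
| 0.3 | 160 | 3.4 |
| 0.5 | 124 | 3.8 |
| 1 | 80 | 4.8 |

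The half-width for 80 first applications is 4.8 points. The precision lost therefore runs from nearly half (ρ = 0) to nothing (ρ = 1).

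**The case against.** The strongest reply is that the condition borrows the label used in sections 9.1 and 9.2.5, where medication errors are called the primary objective. On that reading partial questionnaires qualify and no repeat is lost. It does not hold. It conflicts with the abstract and with sections 8.1 and 8.2. The adjacent definition of the respondent set uses the same phrase, and section 9.7.2.4 uses that set to analyse awareness and intent. Even if accepted, it leaves in place the link to respondents with valid primary-objective answers.

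A second reply is that the intention is clear from the abstract, section 9.7.1, section 9.7.2.4 and the existence of a partial questionnaire, so an analyst would notice. This stands in part. A reader might infer that the sponsor means to drop repeat applications, or that 71% of the data will be lost. The documents support neither: the exclusion looks unintended, and 200 is a ceiling. Nor does every repeat of a patient drop out, because a change of respondent brings a full questionnaire.

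The respondent-level exclusion may also be small. Section 9.6 says that online respondents cannot skip ahead, so gaps would come mainly from paper forms or broken-off sessions, and valid responses need not mean that every item was answered. The protocol gives no frequency.

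Finally, the study is descriptive, the primary endpoint is unaffected, and repeat data are collected either way. That limits the harm but does not make the definition right.

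**Conclusion.** The definition in section 9.7.2.3.1 is wrong as written and contradicts the abstract and sections 9.7.1 and 9.7.2.4. It is a stated rule, not a detail left to the SAP. Read literally, it removes same-respondent repeat applications and all applications of respondents without valid awareness and intent answers.

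The first exclusion costs at most 200 of 280 applications. The widening from 2.8–8.2% to 1.4–12.3% rests on an assumed 5% error proportion and independent applications, and shrinks as within-patient correlation grows. The second exclusion cannot be sized from the protocol. Both can be corrected before analysis, because collection does not change.

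**What to change.** In section 9.7.2.3.1, define the full analysis set of OBI administrations as all administrations reported by participating (enrolled, eligible) respondents whose full or partial questionnaire allows assessment of medication errors, whether or not the awareness and intent items were answered. This drops the requirement that the respondent belong to the full analysis set of respondents, but keeps the link to participating respondents in section 9.7.1, so administrations known only from the HCP's eCRF are not brought in.

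In sections 9.1 and 9.2.5, change the label of the medication-error objective from primary to secondary, to match the abstract and section 8.2. Check that the SAP carries the same definition.

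The cost is three wording changes in the protocol. No extra data are needed, and neither the questionnaires nor the primary analysis changes.

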9.7.2.3.2 Description of Subject Characteristics

HCP and/or respondent representativeness will be assessed by describing the characteristics of HCPs/respondents participating in the study and HCPs/respondents not participating in the study, where the collection of characteristics for those not included in the study is feasible. Number and percentage of respondents included in study population, eligible set, enrolled set and full analysis set of respondents will be described.

A description of respondent demographics and health literacy will be reported.

9.7.2.4 Analysis of the Primary, Secondary and Exploratory Endpoint(s) Primary

Awareness of key safety messages and behavioural intent to carry out recommended actions will be analysed considering individual questions, as well as calculating a composite score. The composite score will be calculated based on the proportion of all awareness and behavioural intent questions with correct responses. Composite scores will be described using descriptive measures for continuous variables, as well as categorical variables using a cut-off point of 70% of correct responses. The composite score will also be presented by whether the respondent received the PAC or not (if occurred), by prior OBI administrations and by the level of health literacy. Awareness and behavioural intent of respondents (composite score) will be also described at

Date: 10 April 2019 Page 31 of 61

HCP/site level and analysed according to site and HCP professional characteristics and prior experience with Neulasta OBI. The primary objective will be analysed in the full sample of respondents who fulfill selection criteria (full analysis set of respondents).

Secondary

In order to assess if the respondent received the PAC, the unique specific question included in the questionnaire will be used. The number and percentage of respondents who have received the PAC will be reported.

This study will help indicate if the PAC is effective as an aRMM based on the assessment described in Section 9.3.2. For the respondents who have received the PAC, the composite score and associated 95% CIs for awareness and behavioural intent will be reported. The selection of a threshold for success is subjective and not based on a priori knowledge, experience, or established scientific criteria in the education or risk communication or evaluation literature. Therefore, the results will be contextualised with other available information.

Device issues identified during OBI administration and subsequent events will be used to identify medication errors. Medication errors will be coded using the Medical Dictionary for Regulatory Activities (MedDRA) version 20 or later and analysed using the medication error Standardised MedDRA Query (SMQ). Subject incidence proportions of medication errors will be summarised. Medication errors will also be presented with respect to the total number of OBI administrations. The subgroups of initial and subsequent OBI applications will be analysed separately to assess the potential impact of subsequent administrations. If differences are not observed, the incidence of medication errors will be reported at overall level. If differences are observed, both subgroups will be separately reported.

Exploratory

The proportion of device issues at the time of OBI application (as reported by the HCP) will be reported at OBI administration and patient level.

9.7.2.5 Sensitivity Analysis

Sensitivity analysis is not planned for this study.

Date: 10 April 2019 Page 32 of 61

9.7.2.5.1 Subgroup Analysis

The awareness and behavioural intent endpoints will also be presented by whether the respondent received the PAC or not, by prior use and monitoring of OBI administrations and by the level of health literacy.

9.7.2.5.2 Stratified Analysis

Not applicable

9.7.2.5.3 Sensitivity Analysis for Residual Confounding and Bias

Not applicable.

9.7.2.5.4 Other Sensitivity Analysis

Not applicable.

9.7.3 Analysis of Safety Endpoint(s)/Outcome(s)

The Medical Dictionary for Regulatory Activities (MedDRA) version 20 or later will be used to code all adverse events reported in the respondent questionnaire. Subject incidence proportions will be presented by system organ class (SOC) and preferred term (PT).

9.8 Quality Control

Standard operating procedures will be applied to ensure quality to all aspects of the study conduct, data management and statistical analysis.

Prior to the study initiation, investigators and all study collaborators will receive specific training on the protocol and on the use of the eCRF. The participant investigators will also be provided personal secure access credentials for the eCRF. Respondents that opt to respond the questionnaire online will be provided with a unique generic link for the respondent questionnaire. In case respondents opt to respond the questionnaire by paper, respondent will send the completed questionnaire to IQVIA in a pre-paid and pre-filled envelope, and data will be directly entered by IQVIA into a specific study database.

Investigators, patients, and their corresponding respondents will have a unique code. The unique code will consist of a combination of the country code, investigator code, and a sequential number of the patient and respondent (this will be detailed in a separate Data Management Plan) (see Section 10.3). This unique code will be generated automatically by the eCRF.

A confidential tracking sheet, listing patient and respondent codes together with patient name and date of birth and respondent name, will be kept by investigators at the study

Date: 10 April 2019 Page 33 of 61

site for identification purposes, if required. Only the investigator and their delegated site team members will have access to the confidential tracking sheet.

All information entered in the eCRF must be traceable to the source documents in the patient's file. The investigator must also keep the original informed consent form signed by the patient and the respondent (a signed copy is given to the patient and to the respondent).

In addition, data generated by this study must be available for inspection upon request by representatives of national and/or local health authorities, sponsor monitors, representatives, and collaborators, as appropriate. The investigator must notify Amgen promptly of any inspections scheduled by regulatory authorities, and promptly forward copies of inspection reports to Amgen.

All study documentation generated in the study, including the final study database and the statistical programming will be kept in a secure server.

The quality control for validating the results will be conducted at five levels:

- 1. At data management level, every efforts will be undertaken to collect complete and valid data:
 - The respondent questionnaire will be developed in English, conceptually reviewed by patients or their caregivers in the UK and will be subsequently translated and linguistically validated with patients/caregivers in each of the participating countries,
 - Verification of the reliability and security of the web questionnaire interface by a qualified web-master for each country,
 - Monitoring of the quality and datasets definition by a qualified data manager.
 In the background of the web questionnaire, real-time checks of the answers
 provided by the respondents will be developed. Non admissible answers (ie,
 incorrect or unusual values, outlying values) will be detected.
 - A database will be created and tested before data entry, two copies of the same database will be prepared to ensure a double data entry. Both databases will be compared until no discrepancies are found.
- 2. At the study database level, final data quality checks will be applied (beyond data management process):
 - Distribution of each variable in order to count the number of missing values and estimate the associated relative percentage,
 - Identification and count of non-analysable questionnaires
 - Any changes in the database will be tracked and documented. The datasets will be stored in a dedicated database. Once data validated and quality checked, the database will be locked.

Page 34 of 61

Protocol Number: 20170701 Date: 10 April 2019

At the statistical analysis level: all data management and statistical analysis programs developed and used in the analysis will be documented. All versions generated will be dated, kept with accompanying documentation and archived. The original database will be stored. A derived database will be created for the new versions of the data in order to include recoding and computing of new variables, especially stratification of continuous variables, combination of modalities for categorical variables, calculation of composite indicators, etc.

- 4. At the results level, a data review will be done to ensure data integrity. A statistical analysis report including all the results will be provided for review and discussion. The final statistical report will take into account the reviewers' comments.
- At the study level, all aspects of the study will be conducted according to the SOPs of IQVIA.

The study documents have been approved by qualified professionals in medical and safety areas of IQVIA.

9.9 **Limitations of the Research Methods**

9.9.1 **Internal Validity of Study Design**

